8.3.6.4 Anemia

Anemia is an AESI and important identified risk for bintrafusp alfa. Notably, there are many reasons for anemia in patients with advanced cancer, therefore a thorough investigation of new anemia cases of unspecified etiology is requested.

For new anemia events items queried may include, but are not limited to, detailed relevant past medical and treatment history, bruising tendency, history of blood transfusions and/or dependency, and a request for an updated eCRF including details such as concomitant medications, all laboratory data, updated dosing information and, recent tumor evaluation scans.

General guidance for anemia management and evaluation:

1. Routine blood test parameters are required in this rollover study per the SoA (see [Table 1](#)).
2. Transfusion should be performed at the discretion of the Investigator based on clinical assessment and considered when the participant experiences severe anemia. An attempt should be made to initiate work-up (as specified below) for the cause of anemia prior to transfusion, if clinically feasible, to not confound this work-up. In general, blood transfusions and erythroid growth factors are permitted as clinically indicated.

Guidance for evaluation of suspected treatment-related anemias is provided in [Table 6](#).

Table 6 Evaluation Guidance of Suspected Anemia

Basic Anemia Evaluation	
1.	CBC with emphasis on red cell indices (e.g., Hgb, hematocrit, MCV, RDW, MCH, MCHC, reticulocytes counts).
2.	If indicated and at clinical discretion, the following should be considered:
a.	Iron studies (TIBC, Ferritin, Fe)
b.	Serum Folate and Vit B12 values
c.	Coagulation factors (PT, PTT, INR)
d.	Fecal occult blood testing
e.	Urinalysis
f.	Hormone panel: TSH, Erythropoietin
g.	Peripheral blood smear for cell morphological assessment
Further Recommendation Based on Suspected Etiology (in Addition to Basic Anemia Testing)	
Suspected hemolysis:	Bilirubin level, LDH, Coombs test, fibrinogen, haptoglobin, d-Dimer Consider Hematology consultation.
Suspected bleeding:	Consider imaging/interventional radiology consultation as indicated Consider endoscopy, as clinically indicated. Consider imaging, as clinically indicated.
Suspected aplastic anemia:	Hematology consultation. Consider bone marrow aspiration/morphologic evaluation.

CBC = complete blood count; Hgb = hemoglobin; INR = international normalized ratio; LDH = lactate dehydrogenase; MCH = mean corpuscular hemoglobin; MCHC = mean corpuscular hemoglobin concentration; MCV = mean corpuscular volume; PT = prothrombin time; PTT = partial thromboplastin time; RDW = red blood cell distribution width; TIBC = total iron binding capacity; and TSH = thyroid-stimulating hormone.

8.3.6.5 Bleeding Adverse Events

Bleeding AEs are AESIs and considered important identified risk.

Mucosal/Non-tumor Bleeding

Participants treated with bintrafusp alfa were commonly reported with mild to moderate mucosal AEs such as epistaxis, hemoptysis, gingival bleeding and hematuria. In general, these reactions resolve without discontinuation of treatment.

For Grade 2 non-tumor bleeding, see Section 7 for general management of Grade 2 treatment-related TEAEs.

For Grade ≥ 3 non-tumor bleeding, study treatment must be permanently discontinued unless an alternative explanation can be identified (such as concomitant use of antithrombotic agents, traumatic event, etc.). In case of alternative explanations for the Grade ≥ 3 bleeding event, study treatment should be held until the event recovers to Grade ≤ 1 . If Grade ≥ 3 bleeding event is observed, regardless of causality with the study intervention, upon resumption of study intervention bintrafusp alfa dose should be reduced by 50% (600 mg once every 2 weeks for participants dosed with 1200 mg, 1200 mg once every 2 weeks for participants dosed with

2,400 mg). Once there is stable resolution and no recurrence of bleeding on reduced dose, Investigator is encouraged to communicate with Medical Monitor on potential dose re-escalation after careful benefit-risk assessment.

For Grade 4 non-tumor bleeding, treatment must be permanently discontinued if no alternative explanation is identified.

In case of rapid decrease of hemoglobin (Hgb), such as a decrease greater than 2.0 g/dL across a 2 weeks period (or 3.0 g/dL across a 3 week period), withhold the subsequent cycles of study intervention until Hgb is stabilized and do a thorough assessment of bleeding (for example, upper and lower GI endoscopy, enhancement CT etc.); if Grade 1 or greater bleeding is observed or suspected, withhold the bintrafusp alfa until the bleeding is resolved/controlled and resume the dose of bintrafusp alfa reduced by 50%. Once Hgb decrease is recovered to \leq Grade 1 or baseline and stably controlled, the Investigator is encouraged to communicate with Medical Monitor to re-escalate the dose. The dose of bintrafusp alfa may be re-escalated to full dose once Hgb is stabilized without further need for blood transfusion in the subsequent cycles. The timing of re escalation may need a case-by-case decision. See Section 8.3.6.4 regarding stabilization of anemia.

Tumor Bleeding

Participants treated with bintrafusp alfa were reported in lower frequencies, with Grade \geq 3 hemorrhages including tumor bleeding. For Grade \geq 2 tumor bleeding, study treatment must be held until the event recovers to Grade \leq 1. If Grade \geq 3 bleeding event had been observed, regardless of causality with the study intervention, upon resumption of the study intervention bintrafusp alfa dose should be reduced by 50%. Once there is stable resolution and no recurrence of bleeding on reduced dose, Investigator is encouraged to communicate with Medical Monitor potential dose re-escalation after careful benefit-risk assessment. Treatment should be permanently discontinued if the Investigator considers the participant to be at risk for additional severe bleeding. In case of rapid decrease of Hgb, see Section 8.3.6.5 Mucosal/Non-tumor Bleeding.

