 - And are willing to re-start bintrafusp alfa treatment if deemed potentially beneficial by the participants' physicians and provided that the parent study protocol permits reinitiation of bintrafusp alfa if a participant discontinued treatment due to toxicity.

Note: Participants who have had AEs requiring permanent treatment discontinuation, like certain immune-related adverse events (irAEs) or certain bleeding events are excluded from participation in the rollover study.

Participants can be transferred from their respective parent bintrafusp alfa study to this rollover study once the primary/main analysis in the parent study has been completed or after discontinuation of study before primary/main analysis has been completed. Participants may also be transferred upon Sponsor decision in case the parent study is terminated for any reason as specified in the parent study protocol and there is a medical need for participants to continue to be treated with bintrafusp alfa that cannot be otherwise supplied. The final decision whether to transfer participants from the parent study rests with the Sponsor.

Brief Summary:

Brief Summary:

This study is designed to provide continuous access to treatment with bintrafusp alfa for eligible participants from ongoing bintrafusp alfa parent studies, and to collect long-term safety and efficacy data:

- Study Duration: All participants in this rollover study will be treated with bintrafusp alfa until meeting defined criteria in the initial study protocol (parent) for discontinuation, until study intervention is commercially accessible and provisioned via marketed product, or until end of study. The study also includes a 5 years survival follow-up after last dose of the study treatment.
- Treatment Duration: Treatment under the rollover protocol according to the interval and dosing schedule in the parent protocol until discontinuation.
- Treatment Frequency: 1200 mg once every 2 weeks; 2400 mg once every 2 weeks; 2400 mg once every 3 weeks. Other dose amount as specified in the participant's parent protocol: once every 2 weeks.
- Bintrafusp alfa is not available through an expanded access program.

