	Day -28 to -1	Day 1 Until Discontinuation of Treatment (\pm 3 days); See Notes	See Notes	Visit 30 Days After Last Treatment (\pm 5 days)	Phone Call 90 Days After Last Treatment (\pm 5 days)	Phone Call Every 12 weeks (\pm 2 weeks)	
Treatment Phase: Participants entering this rollover study on active treatment with bintralusp alfa in a parent study should begin Day 1 treatment under the rollover protocol according to the interval and dosing schedule in the parent protocol.
 
End of Treatment: Visit should be held within 30 days of last treatment for participants discontinuing due to AEs. For all others, visit should be held within 7 days of last treatment or prior to any new antineoplastic therapy, whichever is earlier.

OS and post-treatment anticancer therapies				X	X	X	Survival information (including assessment of any further anticancer therapy) will be collected every 12 weeks (\pm 2 weeks) up to the end of the study (see Section 4.4).
Premedication (optional) and study intervention administration		Day 1 of each cycle					
See Section 6.5.2 and Section 8.3.6 for premedication information
 
Participants on bintralusp alfa will continue treatment until disease progression, unacceptable toxicity, or study withdrawal (see Section 7).
 
Cycle length determined based upon treatment cycle duration from the parent protocol.

Documentation of AEs	X	X	X	X	X		See Section 8.3 and Appendix 4 for safety recording and reporting. The Safety Follow-up and Long-term Follow-up visits may be conducted by telephone calls as necessary, unless there is a medical necessity requiring a clinical visit.
Concomitant medications	X	X	X	X			

AE = adverse event; β -hCG = beta-human chorionic gonadotropin; CR=complete response, CT = computed tomography; ECG = electrocardiogram; ECOG

PS = Eastern Cooperative Oncology Group Performance Status; HBV = hepatitis B virus; HCV = hepatitis C virus; HIV = human immunodeficiency virus;

MRI = magnetic resonance imaging; OS = overall survival; PD = progressive disease; PR = partial response, RECIST = Response Evaluation Criteria in Solid Tumors version 1.1; SD = stable disease, SOC = standard of care; Free T4 = free thyroxine; TSH = thyroid-stimulating hormone.

2 Introduction

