Study Intervention Assignment Method	
For participants who are continuing treatment with bintrafusp alfa and were previously assigned to a bintrafusp alfa dose based on body weight (i.e., a mg/kg dose) in a parent protocol, the Sponsor recommends switching to a flat dose of bintrafusp alfa 1200 mg every 2 weeks as they enroll in the rollover study, after consultation with the Sponsor Medical Lead. However, participants still on active treatment in their respective parent study may, if considered appropriate by the Investigator, opt to continue treatment at their ongoing dose level as they enter this rollover study, with treatment as follows:
 
• Bintrafusp alfa administered on Day 1 of a 2-week cycle at the dose specified based upon the participant's parent protocol and treatment assignment. 
OR
 
• Bintrafusp alfa administered on Day 1 of a 3-week cycle at a dose of 2400 mg. 
Participants who are entering the rollover study after discontinuation of treatment in a parent study will reinitiate bintrafusp alfa as a monotherapy following the same treatment schedule as specified in their original parent protocol. These participants will reinitiate treatment as either:
 
• Bintrafusp alfa administered on Day 1 of a 2-week cycle at a dose of either 1200 or 2400 mg 
OR
 
• Bintrafusp alfa administered on Day 1 of a 3-week cycle at a dose of 2400 mg. 
Restarting treatment as a combination will not be allowed

Involvement of Special Committee(s):	No.
Total Duration of Study Participation per Participant	All participants in this rollover study will be treated with bintrafusp alfa until meeting criteria for discontinuation (see Section 7.1), until study intervention is commercially accessible and provisioned via marketed product, or until end of study (see Section 4.4). The study also includes a 5 years survival follow-up after last dose of the study treatment.
Provisions for Study Extension or Entry into Rollover Studies	This is a rollover study and it is designed to provide continuous access to treatment with bintrafusp alfa for eligible participants from ongoing bintrafusp alfa parent studies, and to collect long-term safety and efficacy data.
Adaptive Aspects of Study Design	Not applicable

4.2

Scientific Rationale for Study Design

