Although not yet approved in any country, bintrafusp alfa has demonstrated meaningful clinical activity across various tumor types and treatment settings. In recent years checkpoint inhibitors have been increasingly used in clinical practice based on superior efficacy and manageable safety profile. Regardless of the tumor type or previous anticancer treatments, responses with bintrafusp alfa appear durable in nature, including ongoing responses > 1 year in several of the cohorts in parent studies. Overall, many responses were still ongoing at the time of database lock of parent studies.

Enrollment in this study will provide continuous access to bintrafusp alfa treatment for participants from parent studies who may experience long-term clinical benefit. Collection of safety data for these participants will provide valuable information to physicians regarding the safety of prolonged treatment with bintrafusp alfa. Participants to be enrolled in this study have been on active bintrafusp alfa treatment without major toxicities requiring treatment discontinuation; therefore, from a long-term perspective it is considered appropriate to continue collection of treatment-related AEs.

Overall survival is the most reliable efficacy endpoint in oncology studies to demonstrate treatment benefit in cancer subjects. Long-term OS data collection will be continued for participants in this study to further support clinical development of bintrafusp alfa.

4.2.1

Participant Input into Design

Not applicable.

4.3

Justification for Dose

In this rollover study, the doses and treatment schedules for bintrafusp alfa (administered as an intravenous [IV] infusion) were selected based on those used in the parent studies and include the following:

- On Day 1 of a 2-week cycle at either a) the flat dose of 1200 mg or b) the dose specified based upon the participant's parent protocol and treatment assignment.
- On Day 1 of a 3-week cycle at a flat dose of 2400 mg.

For participants who are continuing treatment with bintrafusp alfa and were previously assigned to a bintrafusp alfa dose based on body weight (i.e., a mg/kg dose) in a parent protocol, the Sponsor recommends switching to a flat dose of bintrafusp alfa 1200 mg every 2 weeks as they enroll in the rollover study, in consultation with the Sponsor Medical Lead. However, participants still on active treatment in their respective parent study may, if considered

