6.1 Study Intervention(s) Administration

Bintrafusp alfa will be administered as a monotherapy in this rollover study (see [Table 4](#)).

Table 4 Study Intervention

Intervention Name	Bintrafusp alfa
Type	Drug
Dose Formulation^a	Sterile concentrate solution for infusion
Unit Dose Strength(s)	10 mg/mL in single-use glass vials (600 mg provided per vial)
Dose Amount	
 • 1200 mg • 2400 mg • Other dose amount as specified in the participant's parent protocol
Frequency	
 • 1200 mg: once every 2 weeks • 2400 mg: once every 2 weeks • 2400 mg: once every 3 weeks • Other dose amount as specified in the participant's parent protocol: once every 2 weeks
Route of Administration	Intravenous infusion
Dosing Instructions	
 • Flat dose of 1200 mg administered over 1 hour (-10/+20 minutes, i.e., over 50 to 80 minutes) once every 2 weeks. • Flat dose of 2400 mg administered over a minimum of 1 hour (-10/+20 minutes) and up to 2 hours (-10/+20 minutes) once every 3 weeks. • Flat dose of 2400 mg administered over a minimum of 1 hour (-10/+20 minutes) and up to 2 hours (-10/+20 minutes) once every 2 weeks • Other dose amount, as specified in the participant's parent protocol, administered over 1 hour (-10/+20 minutes, i.e., over 50 to 80 minutes) once every 2 weeks.
Use	Experimental
Sourcing	Provided centrally by the Sponsor
Packaging and Labeling	Study Intervention will be provided in vial. Each vial will be packaged and labeled per all applicable regulatory requirements and Good Manufacturing Practice Guidelines.

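### The 50% dose cut after severe non-tumor bleeding is written as 1200 mg every 2 weeks for everyone on 2400 mg; from the 3-week regimen this lowers the weekly dose by only 25%

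*Protocol*

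**What the plan says.** Protocol Section 8.3.6.5 (Mucosal/Non-tumor Bleeding) ends treatment permanently after a Grade 3 or higher event unless another cause is found. If one is found, dosing is held until recovery to Grade 1 or better. The cut on resumption is then set as follows: "by 50% (600 mg once every 2 weeks for participants dosed with 1200 mg, 1200 mg once every 2 weeks for participants dosed with", where the last group is those on 2,400 mg. The starting interval is not mentioned.

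The protocol allows 2400 mg on two intervals. Table 4 in Section 6.1 lists it every 2 weeks and also "2400 mg: once every 3 weeks". Section 4.1 offers the 3-week option both to participants continuing treatment and to those reinitiating it: "Bintrafusp alfa administered on Day 1 of a 3-week cycle at a dose of 2400 mg". Section 4.3 repeats it: "On Day 1 of a 3-week cycle at a flat dose of 2400 mg".

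Elsewhere the interval comes from the parent study. The synopsis says "Treatment under the rollover protocol according to the interval and dosing schedule in the parent protocol until discontinuation", and the Schedule of Activities says "Cycle length determined based upon treatment cycle duration from the parent protocol". Section 6.6 rules out dose modification except for bleeding events, apart from the recommended switch from mg/kg to flat dosing. Section 8.3.6.5 is therefore the only place where a site can look for the reduced regimen.

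Two other rules in Section 8.3.6.5 also call for a 50% reduction. One is triggered by a rapid hemoglobin fall, "a decrease greater than 2.0 g/dL across a 2 weeks period (or 3.0 g/dL across a 3 week period". If bleeding of Grade 1 or more is then seen or suspected, the site must "withhold the bintrafusp alfa until the bleeding is resolved/controlled and resume the dose of bintrafusp alfa reduced by 50" percent. The other applies on resumption after tumor bleeding of Grade 3 or higher. Neither names a regimen or an interval.

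**The concern.** A single line covers two different starting regimens. It suits 2400 mg every 2 weeks. Applied to 2400 mg every 3 weeks, it changes the interval as well as the infusion, and the two changes pull in opposite directions. The protocol does not say that the cycle is meant to change, and gives no reason why this group should keep a larger share of its weekly dose.

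At stake is the restart dose after a severe bleed, and the protocol classes bleeding as an important identified risk. A site that applies the written line gives 1200 mg every 2 weeks. A site that applies the general 50% and keeps the parent cycle, as the synopsis and Schedule of Activities suggest, gives 1200 mg every 3 weeks. Each could defend its choice from the text. In the non-tumor bleeding rule the Medical Monitor is mentioned for re-escalation, not for choosing the reduced regimen.

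**Working it through.** **Inputs.** Starting regimens are from Table 4 (Section 6.1): 1200 mg every 2 weeks, 2400 mg every 2 weeks, 2400 mg every 3 weeks. Reduced regimens are from Section 8.3.6.5: 600 mg every 2 weeks from 1200 mg, and 1200 mg every 2 weeks from 2,400 mg. The parent-cycle alternative, 1200 mg every 3 weeks, is half the infusion on the interval that the Schedule of Activities assigns.

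**Formulas.** Weekly dose = mg per infusion / interval in weeks. Weekly cut = 1 − (new weekly dose / old weekly dose). Per-infusion cut = 1 − (new mg / old mg).

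**The plan's own 50% on the 2-week regimens.**
- 1200 mg every 2 weeks: 1200/2 = 600 mg/week, reduced to 600/2 = 300 mg/week. Weekly cut 1 − 300/600 = 50%; per infusion 1 − 600/1200 = 50%.
- 2400 mg every 2 weeks: 2400/2 = 1200 mg/week, reduced to 1200/2 = 600 mg/week. Weekly cut 1 − 600/1200 = 50%; per infusion 1 − 1200/2400 = 50%.

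The stated 50% is reproduced on both measures.

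**The same line applied to 2400 mg every 3 weeks.** The starting weekly dose is 2400/3 = 800 mg.

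| Regimen on resumption | mg/week | Per-infusion cut | Weekly cut | 12-week total |
|---|---|---|---|---|
| As written: 1200 mg every 2 weeks | 1200/2 = 600 | 50% | 1 − 600/800 = 25% | 6 × 1200 = 7200 mg |
| Half dose on parent cycle: 1200 mg every 3 weeks | 1200/3 = 400 | 50% | 1 − 400/800 = 50% | 4 × 1200 = 4800 mg |

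The 12-week total before the bleed is 4 × 2400 = 9600 mg. The two regimens differ by 600 − 400 = 200 mg/week, a ratio of 600/400 = 1.5.

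**Can the interval be reconciled elsewhere?** The dosing window in Section 6.6 is ±3 days, which cannot absorb a 7-day difference in cycle length. The hemoglobin rule sets its windows at 2 and 3 weeks, so Section 8.3.6.5 does have 3-week schedules in view. No section gives a reduced 3-week regimen or explains a move from a 3-week to a 2-week cycle.

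**The case against.** The strongest reply is that the rule is explicit and does what it says. It reduces the dose, Table 4 lists dose amount and frequency separately, and 2400 to 1200 mg is exactly 50%. As the specific rule for bleeding, it would ordinarily prevail over a synopsis line and a general schedule note. The every-2-weeks wording may also be deliberate: Section 4.3 bases 1200 mg every 2 weeks on the recommended Phase II dose, and Section 2.3.1 draws its risk analysis from 765 participants on that regimen. By contrast, 1200 mg every 3 weeks appears nowhere in the documents.

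Much of this stands. The per-infusion cut is 50%, and the documents do not show which interval the sponsor intended. It does not explain why one group alone changes cycle. Nor does it explain why that group restarts on 1200 mg every 2 weeks, while a participant who bleeds on that same regimen is cut to 600 mg.

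A reader might also infer more than the documents support:
- That the 3-week group has been left out. It has not; the words cover every participant on 2,400 mg. The fault is that they do not separate the two intervals.
- That the three bleeding rules contradict one another. The hemoglobin and tumor-bleeding rules are silent on interval, which is not a contradiction.
- That a participant could restart on more drug than before. Either regimen lowers the weekly dose.

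There are partial safeguards. Section 7.1 brings in the Medical Monitor for exceptions after recurrent treatment-related Grade 3 events and when two or more doses are missed for an adverse event. Section 8 sends immediate safety concerns to the Sponsor. None of these names the reduced regimen.

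**Conclusion.** The point holds as an unexplained interval change in a safety dosing rule. Followed as written, participants on 2400 mg every 3 weeks have their weekly dose cut by 25% (800 to 600 mg), while both 2-week flat regimens are cut by 50%. Keeping the parent cycle would give 400 mg/week.

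The 25% figure assumes that weekly dose is the relevant measure and that the site applies the written line. Measured per infusion, the cut is 50% for all three flat regimens.

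The reach is unknown and probably small. The synopsis expects at least 10 participants, and the documents do not say how many are on the 3-week regimen. Grade 3 or higher non-tumor bleeding leads to resumption only when another cause is found. The effect is on individual dosing; no planned analysis changes. It should be fixed because the instruction applies after a severe bleed and the correction is cheap.

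**What to change.** In Section 8.3.6.5, replace the parenthesis with a list by starting schedule:
- from 1200 mg every 2 weeks: 600 mg every 2 weeks;
- from 2400 mg every 2 weeks: 1200 mg every 2 weeks;
- from 2400 mg every 3 weeks: 1200 mg every 3 weeks, that is, half the dose on the unchanged parent interval;
- from any other parent-protocol dose: half that dose on the parent interval.

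If the sponsor does intend 1200 mg every 2 weeks for the 3-week group, give it a separate line with the reason, and state that the cycle length changes. Refer to the list from the hemoglobin-drop and tumor-bleeding rules.

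The cost is one sentence and two cross-references, by amendment or clarification letter. Table 4 stays as it is, and no procedure is added.

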- PD per RECIST v1.1, with the exception that participants receiving treatment may continue post PD if the participant's Eastern Cooperative Oncology Group Performance Status (ECOG PS) has remained at least stable, and if in the opinion of the Investigator, the participant will benefit from continued treatment (See [Section 7.1.2](#)).
- Unacceptable toxicity

- Drug must not be given to a known pregnant participant (see to [Appendix 3](#))
- Use of a prohibited concomitant drug, as defined in [Section 6.5.3](#) if discontinuation is considered necessary by Investigator/Sponsor.

Any treatment-emergent AE, especially of Grade 4 or recurrent event of Grade 3, that is assessed as related to bintrafusp alfa may require treatment interruption or permanent discontinuation of bintrafusp alfa treatment.

Grade 4 treatment-related TEAEs: Any Grade 4 treatment-related TEAEs require permanent treatment discontinuation, except:

- a. Endocrinopathies that have been controlled by hormone replacement,
- b. Isolated laboratory values out of normal range that do not have any clinical correlation. Discuss with Medical Monitor regarding work-up, management, and treatment continuation versus hold versus discontinuation for isolated Grade 4 laboratory abnormalities,
- c. If an alternative explanation is identified for Grade 4 non tumor bleeding.

Grade 3 treatment-related TEAEs: Participants with any recurrent Grade 3 treatment-related TEAEs should be permanently discontinued. **Exceptions** may be considered for the following after discussion with Medical Monitor (see also relevant management guidance sections):

- a. Transient Grade 3 flu-like symptoms or fever that is controlled with medical management.
- b. Transient Grade 3 fatigue, local reactions, headache, nausea, emesis that resolves to Grade ≤ 1 or baseline.
- c. Tumor flare phenomenon defined as local pain, irritation, or rash localized at sites of known or suspected tumors.
- d. Any Grade ≥ 3 drug-related amylase or lipase abnormality that is not associated with symptoms or clinical manifestations of pancreatitis.
- e. Grade 3 hemoglobin (Hgb) decrease (< 8.0 g/dL) that is clinically manageable with blood transfusions or erythroid growth factor use.
- f. Increases ECOG PS ≥ 3 that resolves to ≤ 2 by Day 1 of the next infusion (i.e., infusions should not be given if the ECOG PS is ≥ 3 on the day of treatment and should be delayed until ECOG PS ≤ 2).

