- g. Keratoacanthoma (KA) and cutaneous squamous cell carcinoma (cSCC).
- h. Grade 3 non tumor bleeding requiring intervention or hospitalization if alternative explanation can be identified (such as concomitant use of antithrombotic agents, traumatic event, etc.).

If persistent Grade 3 treatment-related AEs (excluding endocrinopathies controlled with hormone replacement therapy) either do not resolve or improve to Grade 1 within 12 weeks after last dose of study intervention, treatment must be permanently discontinued. If a Grade 2

treatment-related TEAE improves to Grade ≤ 1 or completely resolves by the day before the next infusion, study intervention may be continued.

Grade 2 treatment-related TEAE

If a Grade 2 treatment-related TEAE does not improve to Grade 1 or completely resolve by the day before the next infusion, but it is manageable and/or not clinically relevant, the Medical Monitor should be consulted to assess if it is clinically reasonable to administer the following infusion. In any case, if ≥ 2 doses are missed due to AE, the Medical Monitor should be consulted.

Immune-related AEs, IRRs, anemia, TGF β inhibition mediated skin reactions, and bleeding AEs

Permanent study intervention discontinuation may be recommended, so the relevant section must be reviewed:

- For suspected irAEs, general guidance and management are provided in [Section 8.3.6.2](#). Recommended guidance and management for specific irAEs as per published guidelines is provided in the current National Comprehensive Cancer Network (NCCN) guideline available at <http://www.nccn.org>.
- IRR and hypersensitivity reaction management guidance are presented in [Section 8.3.6.1](#).
- Anemia management guidance is presented in [Section 8.3.6.4](#).
- TGF β inhibition mediated skin reactions management guidance is provided in [Section 8.3.6.3](#).
- For guidance and management of bleeding AEs, see [Section 8.3.6.5](#).

If study intervention is permanently discontinued, the participant will remain in the study to be evaluated for the End of Treatment and Safety Follow-up. The Schedule of activity (see [Table 1](#)) indicates data to be collected at the time of discontinuation of study intervention and follow-up and for any further evaluations that need to be completed.

In case of discontinuation from the study intervention:

- The day of End of Treatment will correspond to the day of withdrawal (or within 7 days) for further details refer to [Table 1](#).

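### Section 8.3.6.5 gives opposite instructions, permanent stop and resume at half dose, for an unexplained Grade 3 or higher non-tumor bleed with a rapid hemoglobin fall

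*Protocol*

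**What the plan says.** Two rules in Protocol Section 8.3.6.5, both under Mucosal/Non-tumor Bleeding, matter here.

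- **Grade rule.** For non-tumor bleeding of Grade 3 or higher, "study treatment must be permanently discontinued unless an alternative explanation can be identified". The section says it again for the highest non-fatal grade: "For Grade 4 non-tumor bleeding, treatment must be permanently discontinued if no alternative explanation is identified". Where another cause is found, treatment is held until recovery to Grade 1 or lower and then resumes at half dose.
- **Hemoglobin rule.** The trigger is a rapid fall, for example more than 2.0 g/dL over 2 weeks or 3.0 g/dL over 3 weeks. The site holds treatment and looks for bleeding, and "if Grade 1 or greater bleeding is observed or suspected, withhold the bintrafusp alfa until the bleeding is resolved/controlled and resume the dose", reduced by 50%. Later, "The dose of bintrafusp alfa may be re-escalated to full dose once Hgb is stabilized without further need for blood transfusion".

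Section 7.1 adds general stopping rules. Related Grade 4 events require a permanent stop, with a bleeding exception only as follows: "If an alternative explanation is identified for Grade 4 non tumor bleeding". For Grade 3, "Participants with any recurrent Grade 3 treatment-related TEAEs should be permanently discontinued". The bleeding item on the list of possible exceptions is "Grade 3 non tumor bleeding requiring intervention or hospitalization if alternative explanation can be identified". Persistent related Grade 3 events are covered too: if they "either do not resolve or improve to Grade 1 within 12 weeks after last dose of study intervention, treatment must be permanently discontinued". For bleeding events, Section 7.1 then sends the reader to Section 8.3.6.5.

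**The concern.** The lower bound in the hemoglobin rule is Grade 1 and there is no upper bound, so Grades 3 and 4 fall inside it. The sentence does not ask whether another cause was found, and it does not exempt participants who have already met the permanent-stop rule.

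The overlap is not contrived. Severe bleeding is an obvious cause of a hemoglobin fall of more than 2 g/dL, and the paragraph itself anticipates participants who needed transfusion. A site that finds the bleed during the hemoglobin work-up is already reading this paragraph and could take it as the governing instruction.

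Bleeding is listed as an important identified risk in Protocol Section 2.3.1. A site following the hemoglobin rule would re-dose a participant whom the grade rule says must stop for good. SAP Section 10.2.1 also counts failure to withdraw a participant who meets withdrawal criteria as an important protocol deviation. A site could commit one while following the literal text.

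**Working it through.** There is no plan figure to reproduce and no statistical formula applies. The check sets the two rules side by side for every kind of non-tumor bleed with the hemoglobin trigger met, then asks what Section 7.1 resolves.

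**Step 1. Cases.** Grades 1 to 4, each explained or unexplained: 4 × 2 = 8.

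| Non-tumor bleed with rapid hemoglobin fall | Cases | Grade-based rule | Hemoglobin rule | Conflict |
|---|---|---|---|---|
| Grade 1, explained or not | 2 | No specific action | Hold, resume at 50% | No |
| Grade 2, explained or not | 2 | General Grade 2 guidance in Section 7 | Hold, resume at 50% | No; the hemoglobin rule is stricter |
| Grade 3 or 4, explained | 2 | Hold to Grade ≤ 1, resume at 50% | Hold, resume at 50% | No; broadly consistent |
| Grade 3, unexplained | 1 | Permanent stop | Hold, resume at 50% | **Yes** |
| Grade 4, unexplained | 1 | Permanent stop | Hold, resume at 50% | **Yes** |

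The rules conflict in 2 of 8 cases. The earlier sentence on a 50% reduction after any Grade 3 or higher bleed is not part of the conflict, because it applies only once treatment is being resumed. The hemoglobin sentence has no such condition.

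**Step 2. What Section 7.1 resolves.**

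- *Unexplained Grade 4.* Related Grade 4 events stop, and bleeding escapes only if another cause is identified. Appendix 4 ties an unrelated classification to an available alternative explanation, so an unexplained bleed would normally be classed as related. This case is settled as a stop.
- *Unexplained Grade 3, recurrent.* Settled as a stop, since the bleeding exception needs an alternative explanation.
- *Unexplained Grade 3, not improved to Grade 1 within 12 weeks.* Settled as a stop.
- *Unexplained Grade 3, first occurrence, recovers.* Neither Grade 3 rule applies. Section 7.1 otherwise says only that a related event may require interruption or discontinuation, and it refers bleeding back to Section 8.3.6.5, where the conflict sits.

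One case is left.

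**Step 3. What the instructions mean for that participant.**

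- Grade rule: 0 mg, permanently.
- Hemoglobin rule: 0.5 × 1200 mg = 600 mg every 2 weeks, or 0.5 × 2400 mg = 1200 mg every 2 weeks for someone dosed at 2400 mg every 2 weeks. Full dose may follow.

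**The case against.** The best reply is that the sentences can be read together. The stop rule is mandatory in wording, specific to grade and stated twice, and Section 7.1 points the same way. The eligibility criteria also treat some bleeding events as requiring permanent discontinuation. On that reading the hemoglobin paragraph governs holding and dose only for participants who have not already been stopped. A careful investigator would probably act that way. But this reading has to supply a condition that the hemoglobin sentence lacks and that the earlier Grade 3 or higher sentence does contain.

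The open upper limit also has a purpose. The Tumor Bleeding paragraph sends rapid hemoglobin falls to this same text, and tumor bleeding of Grade 3 or higher may resume at half dose, as may explained non-tumor bleeding. This stands, and it means the fix must not simply cap the rule at Grade 2.

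There are safeguards. Re-escalation calls for contact with the Medical Monitor and a case-by-case decision on timing, the Medical Monitor is to be consulted when two or more doses are missed for an adverse event, and Section 8 requires immediate safety concerns to go to the Sponsor. These make unsupervised re-dosing less likely. The Medical Monitor steps attach to re-escalation or missed doses, however, not to the first choice between stopping and resuming, and none of the safeguards says which rule prevails.

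Finally, Section 7.1 says discontinuation criteria follow the parent protocols, which were not available for this check. They might settle the point for some participants. That limits what can be said about practice, not about the wording of Section 8.3.6.5.

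**Conclusion.** The concern holds. As written, Section 8.3.6.5 contradicts itself for unexplained non-tumor bleeding of Grade 3 or higher with a rapid hemoglobin fall. Section 7.1 narrows the unresolved part to a first unexplained Grade 3 bleed that recovers. The narrowing at Grade 4 assumes that an unexplained bleed is classed as treatment-related.

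The counts of 2 in 8 and then 1 are counts of situations, not probabilities. The documents give no frequency for the remaining case. Expected enrollment is at least 10 participants with no cap, so the number affected is probably small but is not bounded. No endpoint, analysis set or statistical figure is affected. The point should still be corrected, because a permanent-stop rule for an important identified risk should not depend on sites inferring which of two instructions takes precedence.

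**What to change.** Make resumption at half dose in the hemoglobin paragraph subject to the permanent-discontinuation rule. Suggested text:

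> Resumption at 50% applies to Grade 1–2 bleeding, to Grade ≥ 3 non-tumor bleeding with an identified alternative explanation once recovered to Grade ≤ 1, and to tumor bleeding that may resume under the Tumor Bleeding paragraph. Grade ≥ 3 non-tumor bleeding without an alternative explanation requires permanent discontinuation regardless of Hgb recovery.

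This keeps every resumption the protocol evidently intends and removes only the contradictory one. It costs one or two sentences in an amendment or clarification letter, with no new data or procedures.
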